
Section 7.4.2 Key Secondary Efficacy Analysis
	
The key secondary efficacy variable is the change from baseline to endpoint in the Clinical Global Impression-Severity of Illness (CGI-S) score, as related to agitation. It will be analyzed by the same statistical methodology specified for the analysis of the primary efficacy variable, based on the ITT population. The alpha used in the analysis of this key secondary endpoint is 0.05 (2-sided), if both of the comparisons of the higher dose groups versus placebo in the primary efficacy endpoint are statistically significant under the Hochberg procedure.
 
CCI [REDACTED]
 
[REDACTED]
 
[REDACTED]
 
[REDACTED]
	
The key secondary efficacy variable is the change from baseline to endpoint in the Clinical Global Impression-Severity of Illness (CGI-S) score, as related to agitation. It will be analyzed by the same statistical methodology specified for the analysis of the primary efficacy variable, based on the ITT population. In order to control the overall type I error rate for this key secondary efficacy analysis, a hierarchical testing procedure will be used so that the overall experiment-wise type I error rate is maintained at 0.05. Thus, if the primary efficacy analysis for the CMAI total score (as described in Section 7.4.1) yields a statistically significant result at 0.05 (2-sided) for both of the comparisons of brexpiprazole 1 mg/day and 2 mg/day versus placebo, then the corresponding comparison for this key secondary efficacy variable (CGI-S score) will be tested at an alpha level of 0.05 (2-sided) using another hierarchical testing procedure in the order of brexpiprazole 2 mg/day versus placebo and brexpiprazole 1 mg/day versus placebo. Thus, brexpiprazole 1 mg/day versus placebo will be tested only if brexpiprazole 2 mg/day versus placebo reaches significance at 0.05

Protocol 331-12-283

Location	Current Text	Revised Text
	
CCI [Redacted]
 
[Redacted]
	
(2-sided) for this key secondary efficacy variable. The alpha used in the analysis of this key secondary endpoint is 0.05 (2-sided), if both of the comparisons of the higher dose groups versus placebo in the primary efficacy endpoint are statistically significant under the Hochberg procedure.
 
CCI [Redacted]
 
[Redacted]
 
[Redacted]
 
[Redacted]

CCI [Redacted]
	
[Redacted]
	
[Redacted]

Protocol 331-12-283

Location	Current Text	Revised Text
	
The change from baseline to Week 12/ET in CMAI subscale scores CCI [redacted] will be analyzed using the MMRM model.
	
psychosis subscale score CCI [redacted]
 
...
 
The change from baseline to Week 12/ET in CMAI subscale scores, CCI [redacted]

CCI [redacted]
	
[redacted]
	
[redacted]

Appendix 1 Names of Sponsor Personnel
	
Primary Medical Contact PPD [redacted] PPD [redacted] Development Otsuka Pharmaceutical Development & Commercialization, Inc. [name] Phone: PPD [redacted] Fax: PPD [redacted]
	
Primary Medical Contacts PPD [redacted] PPD [redacted] Otsuka Pharmaceutical Development & Commercialization, Inc. [name] Phone: PPD [redacted] Fax: PPD [redacted]
 
PPD [redacted] PPD [redacted] Otsuka Pharmaceutical Development & Commercialization, Inc. [name] Phone: PPD [redacted] Fax: PPD [redacted]

Protocol 331-12-283

Location	Current Text	Revised Text																																																								

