All AEs (serious and nonserious) reported by the subject must be recorded on the source documents and eCRFs provided by the sponsor *or designee*.

Paragraph 2:

Changed text:

In addition, ~~the sponsor~~ INC Research (refer to Appendix 2) must be notified immediately by telephone or fax of any immediately reportable events according to the procedure outlined below in Section 5.3.

Section 5.3 Immediately reportable Events (IRE)

Added text:

The investigator must immediately report within 24 hours after either the investigator or site personnel become aware of any SAE or potential Hy's law cases (refer to Section 5.4) by telephone or by fax to the sponsor *or designee* as outlined in Appendix 2.

Section 7.1 Sample Size

Protocol 331-12-283

Changed text:

To account for a portion of subjects who discontinue prematurely and whose data may potentially dilute the treatment effect, *approximately* an additional 10% of subjects was added to the sample size, resulting in a sample size of ~~138~~ 140 subjects in ~~the brexpiprazole 2 mg/day, brexpiprazole 1 mg/day, and placebo~~ each treatment groups, which means the total sample size is ~~483~~ 560 subjects [REDACTED]. The sample size was estimated based on [REDACTED] randomization ratio [REDACTED].

Section 7.3 Handling of Missing Data**Changed and added text:**

[REDACTED]

Section 7.4**Changed subheadings:****7.4 ~~Primary and Secondary Outcome Analysis~~ Efficacy Analyses**

Paragraph 1:

Added text:

[REDACTED]

Paragraph 2:

Added text:

The model will include fixed class-effect terms for treatment, trial center, visit week, and an interaction term of treatment by visit week and include the interaction term of baseline by visit *week* as a covariate.

Section 7.4.1**Changed subheading:****7.4.1 Primary Efficacy-~~Outcome~~ Analysis****Section 7.4.2**

Protocol 331-12-283

Changed subheading:7.4.2 Key Secondary ~~Outcome~~ Efficacy Analysis**Section 7.4.3****Changed subheading:**7.4.2 ~~CCI~~**Deleted text:**Other efficacy ~~outcome~~ variables include the following:**Section 8.1 Packaging and Labeling****Changed text:**

The IMP will be supplied as active brexpiprazole tablets or matching placebo tablets. ~~Brexpiprazole and placebo~~ The 0.25 mg/day dose will be supplied as a blister card containing sufficient tablets for 3 (+2) days; the ~~CCI~~ doses will be supplied as weekly blister cards, each containing sufficient tablets for 7 (+ 2) days.

Section 8.2 Storage**Changed text:**

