Protocol 331-12-283

Amendment Number: 3

Issue Date: 07 Jul 2014

PURPOSE:

The sponsor has determined the need for a third formal amendment to the second amendment of the original protocol. This amendment serves to reflect clarifications and additions to study procedures intended to enhance subject safety and accuracy of data. In addition, administrative clarifications were made, including changes to text to enhance readability and consistency, and changes to correct typographical, punctuation, and formatting errors. These changes were minor and do not change the design or content of the protocol, and therefore, are not summarized in this appendix.

The purpose of amending Protocol 331-12-283, issued 16 Dec 2013, was to:

- CCI [REDACTED]
- CCI [REDACTED]
- Allow the inclusion of non-institutionalized subjects.
- Clarify the caregiver/caretaker requirements.
- Modify the Neuropsychiatric Inventory-Nursing Home scale (NPI-NH) by replacing the Occupational Disruptiveness NPI-NH questions with the Distress questions from the Neuropsychiatric Inventory (NPI) for subjects in a non-institutionalized setting.
- Add the Resource Utilization in Dementia (RUD) assessment for both non-institutionalized and institutionalized subjects.
- Increase the number of planned trial centers from 55 to 75.
- Modify inclusion criteria #6 and #7.
- Modify exclusion criteria #8, #13, #14, #31, #32, and #40.
- Remove exclusion criterion #27 (this resulted in renumbering of exclusion criteria #28 through #41).
- Change the analysis of the primary and key secondary endpoints from the Hochberg procedure to a hierarchical testing procedure.
- Add another primary medical contact.
- Change the medical monitor for Europe.

Protocol 331-12-283

BACKGROUND:

These changes to Protocol 331-12-283 Amendment 2 were made to address the potential issue of missing data due to subjects terminating early, as well as on the basis of adjustments considered important to ensure the safety of the subjects enrolled and to facilitate appropriate study implementation and communication.

MODIFICATIONS TO PROTOCOL:

- **Bold and underlined text:** Changed text
- ~~**Bold and strikethrough text:**~~ Deleted text
- ***Bold and italicized text:*** Added text

General Revisions:

All changes by section are provided below.

Sectional Revisions:

Location	Current Text	Revised Text

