
Synopsis Statistical Methods
	
...The primary endpoint will be analyzed using a mixed-effect model repeated measure (MMRM) methodology. The model will include fixed class effect terms for treatment, trial center, visit week, and an interaction term of treatment by visit week and include the interaction term of baseline by visit week as a covariate. The primary efficacy outcome measure is the mean change from baseline to the endpoint in the CMAI total score. Details of sensitivity analyses under the assumption of missing not at random (MNAR) will be provided in the statistical analysis plan (SAP).
 
The primary statistical comparisons of interest are brexpiprazole 2 mg/day versus placebo and brexpiprazole 1 mg/day versus placebo. To protect the experiment wise alpha level at 0.05
	
...The primary endpoint will be analyzed using a mixed-effect model repeated measure (MMRM) methodology. The model will include fixed class effect terms for treatment, trial center, visit week, and an interaction term of treatment by visit week and include the interaction term of baseline values of CMAI total score by visit week as a covariate. The primary efficacy outcome measure is the mean change from baseline (Day 0 visit) to the end of the double-blind treatment period (Week 12 visit) endpoint in the CMAI total score. Details of sensitivity analyses under the assumption of missing not at random (MNAR) will be provided in the statistical analysis plan (SAP).
 
The primary statistical comparisons of interest are brexpiprazole 2 mg/day versus placebo and brexpiprazole 1

Protocol 331-12-283

Location	Current Text	Revised Text
		
CCI
 
[REDACTED]
 
the total number of subjects to be randomized will be approximately 420 (i.e., subjects from the 0.5-mg treatment group will not be included in the efficacy analyses). The sample size was estimated based on a CCI randomization ratio [REDACTED]. [REDACTED]. The randomization will be stratified by center.

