
Protocol 331-12-283

Location	Current Text	Revised Text
		participated in the trial, the 30-day safety follow-up visit will occur as a clinic visit at the investigator's site.

Protocol 331-12-283

[figure not shown]

Figure 3.1-1 Figure Design Schematic

^a CCI [Redacted]

^b CCI [Redacted] *the total*

number of subjects to be randomized will be approximately 420 CCI [Redacted]

Protocol 331-12-283

Location	Current Text	Revised Text

Section 3.2 Treatments
	
Treatment assignments will be obtained by accessing the IVRS or IWRS. Based on the fixed-block, computer-generated randomization, eligible subjects will be allocated in a [redacted] ratio at randomization [redacted].
 
Neither the investigator nor the subject will be aware of the treatment assignment. All doses of brexpiprazole and matching placebo should be taken orally once daily, preferably in the morning, and can be administered without regard to meals. Brexpiprazole should be taken at the same time each day, particularly prior to visits with pharmacokinetic sampling.
	
Treatment assignments will be obtained by accessing the IVRS or IWRS. Based on the fixed-block, computer-generated randomization, eligible subjects will be allocated in a [redacted] ratio at randomization [redacted].
 
Neither the investigator nor the subject will be aware of the treatment assignment. All doses of brexpiprazole and matching placebo should be taken orally once daily, preferably in the morning, and can be administered without regard to meals. Brexpiprazole should be taken at approximately the same time each day, particularly prior to visits with pharmacokinetic sampling.

	
[redacted]
	
[redacted]

	
The first dose of IMP will be administered on the day after the Baseline visit (i.e., Day 1).
 
[redacted]
	
The first dose of IMP will be administered on the day after the Baseline visit (i.e., Day 1).
 
[redacted]

Protocol 331-12-283

Location	Current Text	Revised Text
	
mg/day starting on the day after the Day 3 visit (i.e., Day 4 [+2 days]).
 
 Subjects will remain on this dose until Week 12/Early Termination (ET) (the last day of the Treatment Period). 	
CC mg/day starting on the day after the Day 3 visit (i.e., Day 4 [+2 days])
 
 Subjects will remain on this dose until Week 12/Early Termination (ET) (the last day of the Treatment Period).

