
Section 7.4.1 Primary Efficacy Analysis
	
The primary endpoint will be analyzed using a mixed-effect model repeated measure (MMRM) model. The primary efficacy outcome measure is the mean change from baseline to the endpoint in the CMAI total score. Details of sensitivity analyses under the assumption of missing not at random (MNAR) will be provided in the SAP. ... To protect the experiment-wise 2-sided alpha level at 0.05 when making 2 comparisons of brexpiprazole doses versus placebo, the statistical testing will be carried out using Hochberg's procedure.
 
The statistical comparison will be performed by the MMRM analysis with an unstructured variance covariance matrix for the repeated measures in which the change from baseline to endpoint in CMAI total score will be the dependent variable based on the OC dataset. The model will include fixed class-effect terms for treatment, trial center, visit week, and an interaction term of treatment by visit week and include the interaction term of baseline by visit week as a covariate.
	
The primary endpoint will be analyzed using a mixed-effect model repeated measure (MMRM) model. The primary efficacy outcome measure is the mean change from baseline (Day 0 visit) to the end of the double-blind treatment period (Week 12 visit) to the endpoint CCI [REDACTED] [REDACTED] [REDACTED].
 
... To protect the experiment-wise 2-sided alpha level at 0.05 when making 2 comparisons of brexpiprazole doses versus placebo, the statistical testing will be carried out using Hochberg's procedure a hierarchical testing procedure in the order of 1) comparison of 2 mg/day brexpiprazole versus placebo and 2) comparison of 1 mg/day brexpiprazole versus placebo. Thus, if the test yields a statistically significant result at 0.05 (2-sided) for the comparison of 2 mg/day brexpiprazole versus placebo, then the comparison of 1 mg/day brexpiprazole versus placebo will be tested at an alpha level of 0.05 (2-sided).
 
The statistical comparison will be

Protocol 331-12-283

Location	Current Text	Revised Text

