		
performed by the MMRM analysis with an unstructured variance covariance matrix for the repeated measures in which the change from baseline (Day 0 visit) to endpoint in CMAI total score (at Weeks 2, 4, 6, 8, 10, and 12) will be the dependent variable based on the OC dataset. The model will include fixed class-effect terms for treatment, trial center, visit week, and an interaction term of treatment by visit week and include the interaction term of baseline values of CMAI total score by visit week as a covariate. The primary comparison between brexpiprazole and the placebo arm at Week 12 will be estimated as the difference between least squares (LS) means from the interaction term of treatment by visit week utilizing the computing software SAS procedure PROC MIXED.

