	
baseline visits, subjects must have a Mini-Mental State Examination (MMSE) score of 5 to 22, inclusive, and a total score (frequency x severity) of ≥ 4 on the agitation/aggression item of the NPI-NH. The NPI-NH will be used for both institutionalized and non-institutionalized subjects; however, the Occupational Disruptiveness questions will not be answered for non-institutionalized subjects. Instead, the Distress questions from the Neuropsychiatric Inventory (NPI) will replace the Occupational Disruptiveness questions for non-institutionalized subjects. This neuropsychiatric assessment for non-institutionalized subjects based on the NPI/NPI-NH will hereafter be referred to as "NPI/NPI-NH".
 
Subjects must have been residing at their current location for at least 14 days before screening and be expected to remain at the same location for the duration of the trial. Subjects from a non-institutionalized setting who at any point during the double-blind treatment phase require permanent placement to a nursing home or assisted living facility will be withdrawn from the trial. Subjects who at any point during the double-blind treatment phase transfer from an institutionalized setting to a non-institutionalized setting will also be withdrawn from the trial. In case of a change in the non-institutionalized address or institutionalized address, the investigator should consult with the medical monitor on a case-by-case basis. In case of a brief hospitalization, determination of subject eligibility to stay in the trial must be made based on subject safety by the investigator and INC Research medical monitor. Subjects in an institutionalized setting may receive supervised day passes at the discretion of the investigator; however, overnight passes will not be allowed
	
severity) of ≥ 4 on the agitation/aggression item of the NPI-NH or the Neuropsychiatric Assessment for Non-institutionalized Patients based on the NPI/NPI-NH (hereafter referred to as "NPI/NPI-NH"). The NPI-NH will be used for institutionalized subjects and the NPI/NPI-NH will be used for non-institutionalized subjects.
 
Subjects must have been residing at their current location for at least 14 days before screening and be expected to remain at the same location for the duration of the trial. Subjects who at any point during the double-blind treatment phase transfer from an institutionalized setting to a non-institutionalized setting, or vice versa, will be withdrawn from the trial. In case of a brief hospitalization, determination of subject eligibility to stay in the trial must be made based on subject safety by the investigator and medical monitor. All attempts should be made to maintain the subjects' normal routine with regard to appointments with physicians and overnight accommodations. Subjects in an institutionalized setting may receive supervised day passes at the discretion of the investigator and may also receive supervised overnight passes at the discretion of the investigator as long as such overnight stays are part of the subjects' normal routine.
 
...
 
It is planned that approximately 840 subjects will be screened at approximately 85 trial sites worldwide in order to randomize approximately 420 subjects.

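### Amendment 3 added home-dwelling subjects, but care setting is not in the visible primary MMRM; adding it is nearly costless and could give a modest gain in precision

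*Protocol*

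**What the plan says.** The available text is the protocol's amendment history. The current body of Sections 3.6.1 and 7.4.1 lies in the part not shown, so the latest visible wording is used.

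- **Population.** One stated purpose of Amendment 3 (07 Jul 2014) is "Allow the inclusion of non-institutionalized subjects". Before it, subjects had to live in a residential care facility.
- **Randomization.** Section 3.2 describes fixed-block allocation. The Amendment 3 revision of the Synopsis, Statistical Methods, says "The randomization will be stratified by center". The Amendment 3 row for Section 3.6.1 is redacted.
- **Primary model.** The Amendment 3 revision of Section 7.4.1 lists the terms: "The model will include fixed class-effect terms for treatment, trial center, visit week, and an interaction term of treatment by visit week". It adds that the model will "include the interaction term of baseline values of CMAI total score by visit week as a covariate". Setting does not appear.
- **Key secondary.** Section 7.4.2 analyzes CGI-S by the same method.
- **Setting is recorded and stable.** Section 3.3, as revised in Amendment 4, uses it to choose the instrument: "The NPI-NH will be used for institutionalized subjects and the NPI/NPI-NH will be used for non-institutionalized subjects". A subject who moves from one setting to the other during treatment is withdrawn (Sections 3.3 and 3.8.3).
- **Amendment 4.** Its visible list of purposes names no change to the strata or the primary model.

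**The concern.** Amendment 3 changed the population and rewrote the primary analysis together, yet the new population factor did not enter the model. Setting is a natural covariate. It is known for every subject at baseline and cannot change on treatment. It may also bear on how the CMAI is obtained: under Section 3.7.2 an institutional caregiver gathers information from several shifts of staff, while a home caregiver may gather it from the caretaker or others.

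Some centers may hold both settings, for instance those that enrolled before and after Amendment 3. There the center term cannot separate the two, and any difference in CMAI change between settings stays in the residual. What is at stake is precision at Week 12. A secondary reason, which cannot be sized from the documents, is that withdrawal on a change of setting makes setting a plausible correlate of dropout. Conditioning on it would then support the missing-at-random assumption behind an observed-case MMRM.

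**Working it through.** **Inputs from the protocol.** 140 per arm after adding about 10% (Section 7.1, Amendment 1 log); three efficacy arms and about 420 randomized (Amendment 3); about 85 sites (Amendment 4); two-sided 0.05; six post-baseline visits.

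**The plan's own figure.** 3 × 140 = 420 agrees, and 126 / 0.9 = 140 is consistent with the 10% allowance. The power calculation itself cannot be reproduced, because the effect size, SD and power are not visible.

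**Assumptions.** 126 evaluable per arm and 85% power. These imply δ/SD = √(2/126) × (1.960 + 1.036) = 0.378. Let D be the difference in CMAI change between settings in SD units (0.2 to 0.5), and w the within-center variance of the setting indicator. w = 0 means each center has one setting; w = 0.25 means an even mix in every center.

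**Gain.** Adjustment multiplies the residual variance by r = 1 − wD², so power = Φ(2.996/√r − 1.960).

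| w | D = 0.2 | D = 0.3 | D = 0.5 |
|---|---|---|---|
| 0 | 85.0% | 85.0% | 85.0% |
| 0.05 | 85.1% | 85.2% | 85.4% |
| 0.15 | 85.2% | 85.5% | 86.3% |
| 0.25 | 85.4% | 85.8% | 87.2% |

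Example: w = 0.25 and D = 0.5 give r = 0.9375, then 2.996/0.968 − 1.960 = 1.135, and Φ = 87.2%.

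**Cost if setting is not prognostic.**
- Simple bound at one visit: residual df = 420 − 3 − 84 − 1 = 332. One added parameter inflates the variance by about 1 + 1/332 = 1.003, and power becomes Φ(2.996/√1.003 − 1.960) = 84.9%.
- Full repeated-measures design: the generalized least squares variance of the Week 12 contrast was computed with and without setting and setting by visit (420 subjects, 85 centers, six visits, blocks of three, serial correlation 0.5 or 0.8; block size and correlation assumed). Average inflation was about 0.2% with settings mixed within centers and 0.02% or less with settings nested in centers. An inflation of 0.2% takes 85.0% to 84.9%. The largest inflation in any single simulated allocation was 0.7%, about 0.2 power point.

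**Validity without the term.** A single-visit simulation with center fixed effects (D = 0.3, 400 runs per case) gave a mean null estimate of 0.001 SD when mixed and 0.005 SD when nested. When mixed, null rejection was 5.8% without setting and 5.5% with it, and the standard error fell from 0.123 to 0.122. When nested, rejection was 7.0% both ways, because the setting term was fully aliased with center. The Monte Carlo standard error is about 1.1 points, so all of these are compatible with 5%.

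**The case against.** The strongest reply is that leaving out a baseline covariate breaks nothing in a randomized trial. That stands. So does the point about center: with about 420/85 ≈ 5 subjects per site, many sites may recruit from a single setting. The setting main effect is then aliased with center. Five of the six setting-by-visit parameters can still be estimated, because the model has no center-by-visit term, but the gain is negligible. Baseline CMAI by visit is already in the model and may take up part of any difference in severity.

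A second reply is that six parameters cost 0.6 to 0.7 power point, which would cancel the gain at D = 0.2 or 0.3. This does not stand. That figure charges all six parameters to one contrast, as if they were all estimated from Week 12 data. The variance of the contrast in the actual design rises by only about 0.2%.

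A third reply is the missing text. The stratification statement rests on the Synopsis, because the revised Section 3.6.1 is redacted. That limits how firmly one can say setting is not a stratum.

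A reader might also infer that setting fixes who the informant is, who gives the drug, and the eligibility score. The protocol does not support this. An institutionalized subject's caregiver may be staff, family, a friend or a hired professional (Section 3.3.1.2). A caregiver may give the drug in either setting (Section 3.12). Eligibility uses frequency times severity on the agitation/aggression item with the same cut-off on both NPI forms, whose item domains are identical (Section 3.7.2.6).

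**Conclusion.** The point holds as a low-cost refinement. In the visible text, setting entered the population in Amendment 3 and is neither a model term nor a stated stratum. Adding it would change power by between roughly −0.1 point (setting not prognostic) and +2.2 points (evenly mixed within centers, D = 0.5). The setting split, its prognostic strength, the design power and the degree of mixing within centers are all assumptions.

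Two stronger readings should be resisted. First, a reader might compute a chance imbalance between arms: with 140 per arm and a 50:50 mix, the SD is √(2 × 0.25/140) = 6.0 percentage points, with a 95% limit of 11.7. It would be wrong to call the resulting shift bias. It is sampling variation already reflected in the standard error, and the figure ignores blocking by center. Second, a reader might conclude that no check of the effect by setting is planned. The documents cannot show that: later analysis rows are redacted, and subgroup tables commonly sit in the SAP.

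**What to change.** Before unblinding, add baseline setting (institutionalized / non-institutionalized) and setting by visit week to the MMRM in Section 7.4.1, and state that the same terms apply to CGI-S in Section 7.4.2. If the sponsor prefers the present model, record why center is considered sufficient, for example because nearly all centers recruit from one setting.

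The change needs no new data and no extra subjects. It uses 1 df per visit, with an expected loss of about 0.1 power point or less if setting proves unrelated to outcome. These terms improve precision only. They do not test whether the treatment effect differs by setting, which is a separate question that the SAP may already cover.
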